9.4.2. Vital Signs

- Heart rate (HR), respiratory rate, systolic and diastolic blood pressure (BP), and temperature will be assessed; the method for measuring temperature will be per the site's preference.
- BP and HR measurements will be assessed in the sitting position with a completely automated device. Manual techniques will be used only if an automated device is not available.

Relamorelin

- BP and HR measurements should be preceded by at least 3 minutes of rest for the participant in a quiet setting without distractions (eg, television, cell phones).
- Vital signs are to be taken before blood collection for laboratory tests.

9.4.3. Electrocardiograms

- Single 12-lead ECG will be obtained as outlined in the SoA (see Section 2) using an ECG machine that automatically calculates the heart rate and measures PR, QRS, QT, and QTc intervals. Refer to Section 8.1 for QTc withdrawal criteria; also see Section 9.2.7.3 for Major Adverse Cardiovascular Events.

9.4.4. Clinical Safety Laboratory Assessments

- See [Appendix 2](#) for the list of clinical laboratory tests to be performed and refer to the SoA (Section 2) for the timing and frequency.
- The investigator must review the laboratory report, document this review, and record any clinically relevant changes occurring during the study in the AE section of the eCRF. The laboratory reports must be filed with the source documents. Clinically significant abnormal laboratory findings are those that are not associated with the underlying disease, unless judged by the investigator to be more severe than expected for the participant's condition.
- All laboratory tests with values considered clinically significantly abnormal during participation in the study or within 30 days after the last dose of study treatment should be repeated until the values return to normal or baseline or are no longer considered clinically significant by the investigator or MSP.
 - If such values do not return to normal/baseline within a period of time judged reasonable by the investigator, the etiology should be identified and the sponsor notified.
 - All protocol-required laboratory assessments, as defined in [Appendix 2](#), must be conducted in accordance with the laboratory manual and the SoA.
 - If laboratory values from non-protocol specified laboratory assessments performed at the institution's local laboratory require a change in participant management or are considered clinically significant by the investigator (eg, SAE or AE or dose modification), then the results must be recorded in the eCRF.

Relamorelin

9.4.5. Hormonal Assessments

In a subset of participants (approximately 100 in total), at a subset of sites, investigation of the effects of study treatment on levels of hormones potentially affected by relamorelin will be carried out. These hormones are GH, insulin-like growth factor-1 (IGF-1), insulin, glucagon, c-peptide, adrenocorticotrophic hormone (ACTH), and cortisol. The participants will be those who will undergo the PK assessment at selected sites. A single fasting blood specimen will be obtained for measurement of the hormones and fasting blood glucose (FBG) at the visits noted in the SoA (Section 2).

9.4.6. Self-monitoring of Blood Glucose

Participants will be strongly encouraged to carry out self-monitoring of blood glucose (SMBG) at home in order to achieve and maintain optimum glucose control during the study. This is almost always required by patients with T1DM and is good clinical practice in patients with T2DM. Sponsor may provide each participant with a glucose monitor, test strips, and all supplies necessary for testing finger-stick capillary blood glucose. It is recommended that this be done twice daily, pre-breakfast (fasting) and approximately 2 hours post-lunch or dinner (whichever is the larger meal).

Information from SMBG, in addition to that provided by values of HbA1c, and FBG, will be available to investigators for decision-making regarding adjustment of diabetic medications, diet, and exercise (or, alternatively, for decision-making regarding referral of the patient to his/her health care provider for the same purpose).

9.5. Pharmacokinetics

Sparse plasma samples of approximately 2 mL per sample will be collected at a subset of sites on a subset of participants to estimate concentrations of relamorelin. These sites will be selected by the sponsor to ensure the appropriate sample handling requirements can be met. In total, approximately 100 participants will be recruited to provide sparse samples.

The dosing of relamorelin and samples collected will occur at the following intervals:

- At Visit 3, administration of the first dose of study treatment will occur at the site, with the time and date recorded. PK samples will be collected within 0.5 hours before dose administration, between 0.5 hours and 1 hour after dose administration, and between 1.5 hours and 3.0 hours after dose administration.
- At Visit 4, Visit 5, Visit 6, and Visit 7, participants are to administer the morning dose of study treatment at home, and provide the site with the date and time of the dose administration. During these visits, a single PK sample will be collected between 0.5 hours and 6.0 hours after dose administration, dependent on the timing of the clinic visit. At the Early Termination Visit, a single PK sample will be collected irrespective of the time of the last dose administration.

██████████
Relamorelin

[figure not shown]
In addition, plasma samples of approximately 4 mL will also be collected to assess the formation of anti-relamorelin antibodies in all study participants. Samples will be collected at Visit 3/Baseline, Visit 4, Visit 5, Visit 7, or Early Termination Visit.

9.6. Pharmacodynamics

[figure not shown]
Pharmacodynamic parameters are not evaluated in this study.

9.7. Genetics

Genetics are not evaluated in this study.

A large, solid black rectangular redaction box covers the majority of the page content below the "Genetics" section.

██████████
Relamorelin

Relamorelin

10. Statistical Considerations

10.1. Sample Size Determination

The sample size and statistical power for the DGSSSS endpoint was assessed by simulation. Data were simulated for the DGSSS over time under the assumption of a multivariate normal distribution and based on mean responses in Study RM-131-009 variance - covariance structure (Table 14.1 of the SAP). A missing completely at random (MCAR) dropout rate of 20% by Week 12 was assumed for each treatment.

Vomiting response rates were assumed to be those observed in Study RM-131-009 (26% and 11% for treatment and placebo respectively). Sample size was assessed using the POWER procedure in SAS.

The sample size of approximately 300 participants per arm will provide more than 90% power to reject at least one of the primary null hypotheses using the multiplicity approach described in Section 10.3 of the SAP.

10.2. Populations for Analyses

The analysis populations will consist of participants as defined in [Table 10-1](#).

Table 10-1: Analysis Populations

Population	Definition
Screened	All screened participants who signed the ICF
Intent-to-treat (ITT)	All randomized participants
Modified intent-to-treat (mITT)	All randomized participants with ≥ 1 post-baseline assessment of DGSSD
Pharmacokinetic	All randomized participants who agreed to volunteer for sparse PK collection, and provided > 2 evaluable samples during the double-blind treatment period
Safety	All participants who received ≥ 1 administration of double-blind study treatment

10.3. Statistical Analyses

The SAP will be developed and finalized before database lock and will describe the participant populations to be included in the analyses, and procedures for accounting for missing, unused, and spurious data. This section is a summary of the planned statistical analyses of the primary and secondary endpoints.

Relamorelin

10.3.1. Key Statistical Methodology

The methodologies defined in [Table 10-2](#) apply as specified to individual endpoints defined in this protocol. All statistical tests will be 2-sided hypothesis tests performed at the 5% level of significance for main effects. All CIs will be 2-sided 95% CIs, unless stated otherwise.

Table 10-2: Statistical Methodology

Methodology	Description
Categorical counts	
 Number of participants in individual categories 
 Participants with ≥ 1 qualifying event counted once per individual category
Categorical descriptives	
 Number and percentage of participants in individual categories 
 Participants with ≥ 1 qualifying event counted once per individual category N1 if percentage denominator \neq number of participants in the population (standard percentage denominator) 
 N1 = participants with nonmissing baseline value
Event descriptives	
 Number and percentage of events in individual categories 
 Events counted individually for each instance Percentage denominator = total number of events
Continuous descriptives	
 N1, mean, SD, median, minimum, maximum N1 = participants with nonmissing value
CFB descriptives	
 Continuous descriptives for baseline, postbaseline, and change from baseline (CFB) values N1 = participants with nonmissing values at both baseline and the specified postbaseline analysis visit
Responder	
 Categorical descriptives for responders and nonresponders 
 Nonresponders include: 
 Participants who do not meet responder criteria Participants with no postbaseline values Risk differences and Wald CIs vs [placebo/active comparator] Estimates derived from Cochran-Mantel-Haenszel (CMH) model controlling for factors (treatment group, region) 
 Mantel-Haenszel (MH) odds ratios (ORs) and CIs vs placebo P-values comparing treatment group vs placebo N1 = all participants unless otherwise specified
CFB	
 Continuous descriptives for CFB Estimates derived from mixed-effects model with repeated measures including fixed effects for geographic region, treatment, week, treatment-by-week interaction, as well as baseline and baseline-by-week interaction values as the covariates 
 LS mean and LS mean difference (CIs) between treatment group and placebo P-values comparing treatment group vs placebo

10.3.2. Efficacy Analyses

10.3.2.1. Primary and Secondary Endpoints

[Table 10-3](#) displays the primary and secondary efficacy endpoints that will be analyzed for the mITT population. All other efficacy endpoints and analyses will be defined in the SAP.

Relamorelin

Table 10-3: Primary and Secondary Endpoints

Primary Endpoints	Description	Timing	Methodology
CFB to Week 12 in weekly DGSSS	Change from baseline to Week 12 in weekly DGSSS	Week 12	CFB
Vomiting Responder	Vomiting responder during last 6 weeks of treatment	Last 6-weeks of Treatment Period	Responder
Secondary Endpoints			
Nausea Responder	Nausea responder during last 6 weeks of treatment	Last 6-weeks of Treatment Period	Responder
Abdominal Pain Responder	Abdominal Pain responder during last 6 weeks of treatment	Last 6-weeks of Treatment Period	Responder
Bloating Responder	Bloating responder during last 6 weeks of treatment	Last 6-weeks of Treatment Period	Responder
Postprandial Fullness Responder	Postprandial Fullness responder during last 6 weeks of treatment	Last 6-weeks of Treatment Period	Responder

10.3.2.2. Multiple Comparisons Procedure

To control the overall type-1 error rate of the study, a multiplicity adjustment will be applied to the primary and secondary endpoints. For that purpose, the hypotheses of interest will be grouped into the two families described below:

- Family 1:
 - Hypothesis H1: Comparison of relamorelin versus placebo in the change from baseline to Week 12 in weekly DGSSS
 - Hypothesis H2: Comparison of relamorelin versus placebo in Vomiting response rate
- Family 2:
 - Hypotheses H3-H6: Comparison of relamorelin versus placebo in the response rates of the individual symptoms comprising DGSSS (ie, nausea, abdominal pain, postprandial fullness, and bloating)

The multiple testing will be performed in two Steps as follows:

Step 1: Treatment comparisons to placebo in the DGSSS and vomiting response rates will be performed using the truncated Holm test at $\alpha=0.05$. A truncation parameter of 0.5 will be used.

Relamorelin

Step 2: If any of the comparisons at Step 1 is significant, the treatment comparisons to placebo in the individual symptoms response rates will be performed using the regular Holm test at a level alpha which depends on the unused alpha from Step 1.

Details for other efficacy analyses are provided in the SAP.

10.3.2.3. Missing Data

Participants with a missing weekly value for vomiting frequency or the individual symptoms comprising the DGSSS (ie, nausea, abdominal pain, postprandial fullness, and bloating) during any of the last 6 weeks will be analyzed as a non-responder for the endpoint.

Analysis for 2 primary endpoints based on multiple imputations (MI) as proposed by [Little and Rubin \(1987\)](#) will also be provided MI for weekly vomiting episodes, will be performed under both missing at random and the missing not at random (MNAR) assumptions, and MI for change from baseline in the weekly DGSSS will be performed only under MNAR assumption.

Detailed methods and procedures for the above outlined missing data-derived sensitivity analyses, planned or exploratory, will be documented in the final SAP prior to the study completion.

12.1. Appendix 1: Abbreviations

ACTH	adrenocorticotrophic hormone
ADA	anti-drug antibodies
AE	adverse event
AESI	adverse event of special interest
ALT	alanine aminotransferase
AST	aspartate aminotransferase
BID	twice daily
BMI	body mass index
BP	blood pressure

CDER	Center for Drug Evaluation and Research
CFB	change from baseline
CFR	Code of Federal Regulations
CIOMS	Council for International Organizations of Medical Sciences
CONSORT	Consolidated Standards of Reporting
CSR	clinical study report
DFU	directions for use
DG	diabetic gastroparesis
DGSSD	Diabetic Gastroparesis Symptom Severity Diary
DGSSS	Diabetic Gastroparesis Symptom Severity Score
DILI	drug-induced liver injury
DSMB	Data and Safety Monitoring Board
ECG	electrocardiogram

Relamorelin	
eCRF	electronic case report form
eGFR	estimated glomerular filtration rate
ET	early termination
EU	European Union
FBG	fasting blood glucose
FDA	US Food and Drug Administration
FSH	follicle stimulating hormone
GCP	Good Clinical Practice

GE	gastric emptying
GEBT	gastric emptying breath test
GERD	gastroesophageal reflux disease
GHS1 α	Growth Hormone Secretagogue 1 α
GH	growth hormone
GI	gastrointestinal
GLP-1	glucagon-like peptide-1
GP	gastroparesis
HbA1c	glycosylated hemoglobin A1c
HEOR	health economic outcomes research
HIPAA	Health Insurance Portability and Accountability Act
HR	heart rate
HRT	hormonal replacement therapy
ICF	informed consent form
ICH	International Council on Harmonisation

Relamorelin	
IEC	Independent Ethics Committee
IGF-1	insulin-like growth factor-1
IND	Investigational New Drug Application
INR	international normalized ratio
IRB	Institutional Review Board
IWRS	interactive web response system
MACE	major adverse cardiovascular events
MI	multiple imputations
MMRM	mixed method for repeated measures
MNAR	missing not at random
MSP	medical safety physician
NRS	numerical rating scale

PK	pharmacokinetic
PRO	patient-reported outcome
QTcB	QT interval corrected for heart rate using the Bazett formula
QTcF	QT interval corrected for heart rate using Fridericia formula
RLM	relamorelin
SAE	serious adverse event
SAP	statistical analysis plan

Relamorelin	
SC	subcutaneous(ly)
SF-12v2	12-item Short Form Survey (version 2)
SGLT-1	sodium-glucose co-transporter-1
SGLT-2	sodium-glucose co-transporter-2
SMBG	self-monitoring of blood glucose
SoA	Schedule of Activities
SUSAR	suspected unexpected serious adverse reaction
T1DM	type 1 diabetes mellitus
T2DM	type 2 diabetes mellitus
UDS	urine drug screen

2.2 List of Figures

Figure 4.1–1. RLM-MD-01 / RLM-MD-02 Study Schematic 8

3.0

List of Abbreviations

aCSR	abbreviated clinical study report
AE	adverse event
AESI	adverse event of special interest
ALT	alanine aminotransferase
ALP	alkaline phosphatase
ANCOVA	analysis of covariance
ANOVA	analysis of variance
AST	aspartate aminotransferase
CFB	change from baseline
CI	confidence interval
CMH	Cochran-Mantel-Haenszel
DG	diabetic gastroparesis
DGSSD	Diabetic Gastroparesis Symptom Severity Diary
DGSSS	Diabetic Gastroparesis Symptom Severity Score
DGSSS-SR	DGSSS Study Responder
GEBT	gastric emptying breath test
eCRF	electronic case report form
ECG	electrocardiogram, electrocardiographic
eDiary	electronic diary
EOT	end of trial
ITT	intent to treat
IP	investigational product

LSMs	Least squares means
MAR	missing at random
MCMC	Monte-Carlo Markov chain
MI	multiple imputation
mITT	modified intent to treat
MMRM	mixed-effects model with repeated measures
MNAR	missing not at random
OC	observed cases
OR	odds ratio

PCS	potentially clinically significant
QTc	QT interval corrected for heart rate

QTcB	QT interval corrected for heart rate using the Bazett formula (QTcB = QT/(RR) ^{1/2})
QTcF	QT interval corrected for heart rate using the Fridericia formula (QTcF = QT/(RR) ^{1/3})
RM	rescue medication
RLM	Relamorelin
SAE	serious adverse event
SAP	statistical analysis plan
SE	standard error
SI	Le Système International d'Unités (International System of Units)
SOC	system organ class
TBL	total bilirubin
TEAE	treatment-emergent adverse event
TESAE	treatment-emergent serious adverse event
TFLs	Tables/Figures/Listings
V-SR	vomiting study responder

4.0 **Introduction**

This statistical analysis plan (SAP) provides a more technical and detailed elaboration of the statistical analyses of the efficacy and safety data that will be performed for Study RLM-MD-01 and separately for study RLM-MD-02 as outlined and/or specified in their respective protocols:

- RLM-MD-01: Final protocol (version dated 13 Jul 2017) and the most recent amendment (Amendment 4 dated 08 Feb 2019).
- RLM-MD-02: Final protocol (version dated 3 Oct 2017) and the most recent amendment (Amendment 3 dated 05 March 2019).

Specifications of tables, figures, and data listings for each study are contained in a separate document. [REDACTED]

The study was early/prematurely terminated on 04 September 2020 when the letter explaining termination activities was sent to all investigators. As a result, the original planned full analyses for the study are no longer applicable for the terminated study. Only abbreviated clinical study report (aCSR) for RLM-MD-01 and RLM-MD-02 will be developed.

The statistical analysis plan (SAP) amendment 2 is based on the amendment #1 SAP dated 29 Sep 2020. The major change to the amendment #1 SAP is to add descriptive analyses for the primary and secondary efficacy endpoints for the results posting on ClinicalTrials.gov and EudraCT (European Union Drug Regulating Authorities Clinical Trials Database) and add the COVID-19 data listing. Please refer to Section [19.2](#) Appendix 2 for details of the outlined analyses for the aCSR.

4.1 **Study Design**

Studies RLM-MD-01 and RLM-MD-02 are identical, designed as global, multicenter, randomized, double-blind, placebo-controlled, parallel-group in participants with diabetic gastroparesis.

In each study, approximately 600 eligible participants will be randomly assigned in a ratio of 1:1 to 1 of 2 treatment groups as follows:

[figure not shown]
- Treatment Group 1: Relamorelin (RLM) 10 µg BID (n=300)
- Treatment Group 2: Placebo BID (n=300)

The duration of each study is 18 weeks, including a 4-week Screening Period, a 2-week single blind Run-in Period, and a 12-week Treatment Period:

[figure not shown]
- Run-in Period: Participants who meet initial study entry criteria during the Screening Period will enter a 2-week Run-in Period, during which they will self-administer single-blind placebo twice daily subcutaneously. Using an electronic hand-held device, participants will report their daily symptoms via the Diabetic Gastroparesis Symptom Severity Diary (DGSSD) as well as their overall global impression of status, treatment satisfaction, treatment compliance, and use of rescue medication.
- 12-week Treatment Period: Participants who meet study entry criteria at the end of the Run-in Period, will be randomized 1:1 to blinded treatment with relamorelin 10 µg or placebo, and will continue to use the electronic hand-held device for reporting of their symptoms via the DGSSD as well as their overall global impression of status and change, treatment satisfaction, compliance, and use of rescue medication.

[figure not shown]
Study schematic and schedule of evaluations for Study RLM-MD-01 and Study RLM-MD-02 are presented in [Figure 4.1-1](#) and [Table 4.1-1](#) respectively.

[figure not shown]
Figure 4.1-1. RLM-MD-01 / RLM-MD-02 Study Schematic

[figure not shown]

Participants not meeting certain study entry criteria during Screening Period may be eligible to enter another RLM study (Study RLM-MD-04)

5.0 **Objectives**

For each study, the primary objectives are:

- To compare the efficacy of relamorelin with placebo in participants with DG with respect to a composite of the following core signs and symptoms of DG:
 - Nausea
 - Abdominal Pain
 - Bloating
 - Postprandial fullness
- To compare the efficacy of relamorelin with placebo in participants with DG with respect to vomiting frequency

For each study, the secondary objectives are:

- To compare the efficacy of relamorelin with placebo in participants with DG with respect to the following individual symptoms of the DGSSS:
 - Nausea
 - Abdominal Pain
 - Bloating
 - Postprandial fullness
- To compare the safety of relamorelin with placebo in participants with DG

6.0

Populations for Analyses

6.1

Screened Population

The Screened Population will consist of all participants who sign informed consent.

6.2

Intent-to-Treat Population

The Intent-to-Treat (ITT) Population will consist of all randomized participants (i.e. participants in the Screened Population who are randomized to a treatment group in the study).

6.3

Modified Intent-to-Treat Population

The Modified Intent-to-Treat (mITT) Population will consist of all randomized participants who had at least 1 post-baseline assessment of the DGSSD.

The mITT population will be used for all efficacy analyses. In efficacy analyses, participants will be included in the treatment group based on the treatment they were randomized to (i.e. regardless of the treatment they actually received).

6.4

Safety Population

The Safety Population will consist of all participants who received at least 1 dose of double-blind study treatment.

The Safety population will be used for all safety analyses. In safety summaries, participants will be included in the treatment group based on the treatment they actually received regardless of the treatment they were randomized to. In case a participant receives relamorelin 10 µg and placebo alternatively during the study, the participant will be included in the relamorelin 10 µg group for purpose of safety analyses.

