10.0 Efficacy Analyses

The efficacy analyses will be based on the mITT Population.

Most efficacy parameters will be derived from the DGSSD, a 7-item, patient-reported daily diary designed to assess the severity of 6 core signs and symptoms of DG—nausea, abdominal pain, postprandial fullness, bloating, vomiting, and early satiety—and the frequency of vomiting episodes (Appendix 1). For purposes of the analyses, weekly values will be calculated from the daily e-diary data as described in Section 16.3 of this SAP. For weeks with less than 4 days of available DGSSD data, weekly values will be set to missing.

Baseline values for parameters are derived from the DGSSD collected in the Run-in period, (ie, *Diabetic Gastroparesis Symptom Severity Score (DGSSS: sum of nausea, abdominal pain, postprandial fullness, and bloating), nausea, abdominal pain, postprandial fullness, bloating, early satiety, vomiting frequency and vomiting severity*) following the steps below:

- Weekly value for Week -2 and Week -1 will be the average value of DGSSD in the week (See the analysis week definition for Week -2 and Week -1 in Section 16.2.1);
- Baseline will be the average of the two weekly values of Week -2 and Week -1.

All statistical tests will be 2-sided hypothesis tests performed at the 5% level of significance for main effects. All confidence intervals will be 2-sided 95% confidence interval, unless stated otherwise.

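### The responder endpoints drop randomised participants with no post-baseline diary entry from the denominator, although the plan's missing-data rule already makes them non-responders

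*SAP*

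**What the plan says.** SAP section 6.3 sets one population for efficacy: "The mITT population will be used for all efficacy analyses". SAP 10.0 repeats this, and protocol section 10.3.2.1 says that Table 10-3 "displays the primary and secondary efficacy endpoints that will be analyzed for the mITT population". Protocol Table 10-1 defines mITT as "All randomized participants with ≥ 1 post-baseline assessment of DGSSD". ITT, meaning all randomised participants, is defined too, but the available text uses it only for disposition, demographics and baseline characteristics.

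The missing-data rule for responders is given three times. SAP 10.1.1.2 (vomiting), SAP 10.2 (nausea, abdominal pain, bloating, postprandial fullness) and protocol 10.3.2.3 all make a participant a non-responder if a weekly value is missing in any of the last 6 weeks. The Responder row of protocol Table 10-2 lists "Participants with no postbaseline values" among the non-responders and gives the denominator as "N1 = all participants unless otherwise specified".

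SAP 10.0 adds: "For weeks with less than 4 days of available DGSSD data, weekly values will be set to missing".

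On the study's status, SAP 4.0 says that "the original planned full analyses for the study are no longer applicable for the terminated study", and that the main purpose of SAP amendment 2 was to "add descriptive analyses for the primary and secondary efficacy endpoints for the results posting on ClinicalTrials.gov and EudraCT".

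**The concern.** All five responder endpoints come from the daily diary. A randomised participant with no post-baseline entry is missing all of Weeks 7 to 12, so the plan's own rule gives the answer: non-responder. The mITT definition removes that participant before the rule can apply. This is a post-randomisation exclusion, and the endpoint does not need it.

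The cut-off is also arbitrary. Someone who makes one entry on the evening of Day 1 and then leaves has fewer than 4 diary days in every week, hence no weekly value at all, yet stays in mITT and counts as a non-responder. Someone who leaves before that entry is dropped. Neither has usable weekly data.

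Two consequences follow. Each arm's response rate is raised slightly, and if exclusions differed by arm the comparison would shift as well. The DGSSS change-from-baseline analysis is not affected, because a participant with no post-baseline value contributes nothing to the MMRM.

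**Working it through.** **Inputs.** Planning rates of 26% and 11%, about 300 per arm, and 20% dropout by Week 12 (SAP 14.0); first truncated-Holm critical value of 0.025 (SAP 10.3); 84 treatment days (SAP 16.2.1). The number with no post-baseline diary is not given, so it is varied below.

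**The plan's own figure.** The stated power is above 90% to reject at least one primary hypothesis. Power for vomiting alone at 0.025 is a lower bound on this:

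- null SE = √(0.185 × 0.815 × 2/300) = 0.0317
- alternative SE = √((0.26 × 0.74 + 0.11 × 0.89)/300) = 0.0311
- power = Φ((0.15 − 2.241 × 0.0317)/0.0311) = 99.4%

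The stated figure stands, and this point does not dispute it.

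**How many might be excluded.** Day 1 is both the day of randomisation and the day of first dose (SAP 9.1, 16.2.1). The diary is due every evening (protocol 9.1), and device compliance in the run-in is required for entry (protocol 5.1). Exclusion therefore needs a participant to leave, or to stop using the diary, almost at once. At a constant daily rate, dropout on Day 1 is 1 − 0.8^(1/84) = 0.27%, and 0.0027 × 300 ≈ 0.8 per arm.

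**Effect on the rates.** Assume that 26% and 11% are all-randomised rates, which gives 78 and 33 responders. Every excluded participant is a non-responder, so the mITT rate is responders / (300 − excluded). The z statistic is the pooled two-proportion statistic without region strata, an approximation to the planned CMH test.

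| Excluded (relamorelin, placebo) | Relamorelin | Placebo | Difference (points) | z |
|---|---|---|---|---|
| 0, 0 (ITT) | 26.00% | 11.00% | 15.00 | 4.73 |
| 0.8, 0.8 (base case) | 26.07% | 11.03% | 15.04 | 4.73 |
| 3, 3 (1% per arm) | 26.26% | 11.11% | 15.15 | 4.74 |
| 15, 3 (stress test) | 27.37% | 11.11% | 16.26 | 4.99 |
| 3, 15 (stress test) | 26.26% | 11.58% | 14.68 | 4.51 |

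The stress tests are extreme: 15 participants would be a quarter of the 0.20 × 300 = 60 dropouts planned per arm over the whole 12 weeks.

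**Independent of sample size.** If a share e of an arm is excluded, its rate is inflated by 1/(1 − e): 1.003 at 0.27% and 1.010 at 1%. This holds whatever number had been randomised when the study stopped.

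**If the planning rates instead apply only to participants with diary data.** With 1% per arm lacking a diary, vomiting power at 0.025 is 99.39% in ITT and 99.40% in mITT. With 5% it is 99.15% and 99.21%.

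**Near a boundary.** With hypothetical counts of 52/300 and 33/300, p = 0.0261 and the 0.025 threshold is missed. Removing 6 relamorelin participants and no placebo participants gives 52/294, p = 0.0200, which passes. Removing 15 from each arm gives p = 0.0255. Only unequal exclusion matters.

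**The case against.** The strongest reply is that nothing turns on this. The base case moves the difference by 0.04 points and leaves z at 4.73. Nothing in the documents suggests that exclusions would differ by arm, and the boundary example uses invented counts for a test that no longer applies. All of that stands.

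The practical effect also cannot be confirmed. SAP 4.0 sends the reader to Appendix 2 for the analyses that remain, and Appendix 2 is not in the available text; nor are some other SAP sections, such as 10.4. The posted rates may already use ITT. This stands too, although section 6.3 as worded covers every efficacy analysis.

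There is no contradiction between the documents. The non-responder rule classifies people within an analysis set and does not define the set. The default denominator in Table 10-2 yields to anything specified elsewhere, and protocol 10.3.2.1 specifies mITT. The Table 10-2 entry for participants without post-baseline values could also operate inside mITT, for those with one to three diary days and no weekly value. That is correct, but it underlines how thin the line is between no entry and one entry.

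Finally, a single prespecified set for both primary endpoints is tidy, and SAP 7.0 plans ITT and mITT counts by arm, so a reader could derive the ITT rate. The tidiness is real but does not require the exclusion: the two primary endpoints already handle missing data differently.

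**Conclusion.** The point holds, as a minor improvement. The plan takes a small group of randomised participants out of five responder denominators although its own rule already classifies them. The rates are inflated by a factor of about 1.003 in the base case and 1.010 if 1% per arm are affected. At the planning rates no test decision changes, even under the stress tests.

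These sizes rest on the planning rates being all-randomised rates, on the constant daily dropout rate in the base case, and on the other assumed exclusion counts. Because the study was terminated early, the live consequence is confined to the descriptive rates to be posted, whose population could not be checked.

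**What to change.** Use all randomised participants as the denominator for Vomiting Responder and the four symptom-responder endpoints, and count those with no post-baseline diary data as non-responders. Apply this to the posted response rates. Keep mITT as a supportive set, show the number excluded per arm beside the rates, and leave the MMRM unchanged.

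Two related rules need a sentence each:

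- **SAP 10.1.2.1:** say whether the multiple imputation for vomiting response stays in mITT or also imputes these participants. They bring no new data pattern, because mITT can already contain participants with one to three diary days and all 12 weekly values missing.
- **SAP 16.11:** say whether the minimum of 8 per region is counted on all randomised participants or still on those with post-baseline diary data, with the remaining ITT participants then placed in the resulting pooled regions.

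The cost is wording in SAP 6.3 and 10.0 and protocol 10.3.2.1, plus minor programming for a second population. No new data are needed: the ITT rate is mITT responders divided by the ITT count, and SAP 7.0 already plans both population counts by arm. The downside is slightly lower rates, for example 26.0% and 11.0% instead of 26.3% and 11.1% if 1% per arm are affected.
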